### EQ5D

The EQ-5D is a standardized measure of health status that consists of 5 dimensions (mobility, self-care, usual activities, pain/discomfort, anxiety/depression) each measured on 5 levels (no problems, slight problems, moderate problems, severe problems and extreme problems) and a

#### Page 18 of 22

VAS of the subject's self-rated health. The VAS is scored from 0-100 where 0 corresponds to 'the worst health you can imagine' and 100 to the 'the best health you can imagine'.

The EQ5D is assessed at baseline, week 3 and week 4.

#### **OMERACT-OARSI Responder Criteria**

The OMERACT-OARSI responder criteria (Pham, et al., 2004) are based on the WOMAC pain and function sub-scores and the Patient Global Assessment (PGA) questionnaire.

A subject is defined as a responder if they demonstrate either

- a) High improvement in at least 1 of the WOMAC pain or function sub-scores or
- b) Moderate improvement in at least 2 of the WOMAC pain sub-score, WOMAC function sub-score or PGA.

where high improvement is defined as

- Relative improvement of  $\geq$  50% (i.e. relative change  $\leq$  -50%) from baseline AND
- Absolute improvement of  $\geq 20$  (i.e. absolute change  $\leq -20$ )) from baseline

and moderate improvement is defined as

- Relative improvement of  $\geq 20\%$  (i.e. relative change  $\leq -20\%$ )) from baseline AND
- Absolute improvement of  $\geq 10$  (i.e. absolute change  $\leq -10$ )) from baseline.

and

relative change = percentage change during the study

= ((final score – baseline score)/ baseline score) \* 100

absolute change = absolute change during the study

= final score (normalised) – baseline score (normalised)

In the situation that at least one of the three endpoints (i.e. WOMAC pain and function sub-scores and PGA) required to assess the responder criteria is missing:

- If the available endpoints satisfy the responder criteria, then the subject will be classified as a responder. (e.g. If a subject has high improvement on the WOMAC pain sub-score but the WOMAC function sub-score and PGA are missing then the subject is a responder).
- If the available endpoints do not satisfy the responder criteria AND there is no possibility that they could have been a responder when considering possible values for the missing score(s), then the response will be set to non-response. (e.g. If a subject does not achieve moderate response on either the WOMAC pain sub-score or the PGA and the WOMAC function sub-score missing then the subject is a non-responder).
- If the available endpoints do NOT satisfy the responder criteria BUT the subject could have been a responder depending on the possible values for the missing score(s)), then the

response will be set to missing (e.g. If either of the WOMAN pain or function sub-scores are missing then the response rate will be set to missing).

OMERACT-OARSI responder criteria will be evaluated at weeks 1, 2, 3 and 4.

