#### 1.1.2 Endpoints

The primary endpoint of this study (double-blind treatment groups only) is:

• The change from baseline in WOMAC pain sub-score (questions 1 to 5) in the target knee as evaluated at week 4.

The secondary endpoints of this study (double-blind treatment groups only) are:

- Changes from baseline in WOMAC total score and the WOMAC function and stiffness scores at week 4
- Changes from baseline in constant and intermittent OA pain assessed by ICOAP scores at week 4
- Changes from baseline in WOMAC pain weight-bearing score (questions 1, 2, and 5) and non-weight bearing score (questions 3 and 4) at week 4
- Changes from baseline in physical function assessed by the chair-stand test at week 4
- OMERACT-OARSI responder rate at week 4
- Total dose of rescue medication calculated as the sum of tablets used, based on pill counts
- Time between baseline and first use of rescue medication
- Changes from baseline in WOMAC pain sub-score (questions 1 to 5) between groups receiving AMZ001 QD and BID in the target knee as evaluated at week 4

- Changes from baseline in constant and intermittent OA pain assessed by ICOAP scores between groups receiving AMZ001 QD and BID at week 4
- Changes from baseline in WOMAC pain weight-bearing score (questions 1, 2, and 5) and non-weight bearing score (questions 3 and 4) between groups receiving AMZ001 QD and BID at week 4
- Changes from baseline in physical function assessed by the chair-stand test between AMZ001 QD and BID at week 4
- Changes from baseline in WOMAC total score and the WOMAC function and stiffness scores between AMZ001 QD and BID at week 4.
- Changes from baseline in the impact of OA on daily living as assessed by the PGA score at week 4
- Changes from baseline in work productivity and activity assessed by the WPAI at week 4
- Changes from baseline in quality of life assessed by the EQ5D at week 4

The safety endpoints of this study are:

- Nature, incidence and severity of AEs
- Changes in laboratory safety parameters, vital signs, 12-lead ECG parameters and weight
- Nature, incidence and severity of skin reactions on the application site

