### 2.2 Determination of sample size

The power is determined from expected changes in the primary endpoint of the change from baseline in pain as evaluated by the WOMAC pain sub-score. The power calculation is based on data from a 4-week double-blind diclofenac sodium 2 % topical solution treatment study in knee osteoarthritis patients (Wadsworth et al. 2016). In this study using the WOMAC LK (Likert) 3.1 scale (0-4 for each question), a decrease from baseline in WOMAC pain sub-score (5 questions) was recorded in the diclofenac treatment group of 4.5 (SD 4.5) and in the placebo group 3.6 (SD 4.2).

The estimated common SD of 4.4 in the LK 3.1 scale can be converted to a SD of 4.4 \* 2.5 = 11 in the NRS scale. Calculations based on a series of assumptions are shown below in Table **2**. With the assumptions of the SD of 11 (NRS scale), 120 subjects enrolled in each of the double-blinded treatment arms, 10 % dropout rate, normal distribution, 5 % level of significance two-sided, 80 % power, the study will be powered to detect a treatment difference in WOMAC pain sub-score between AMZ001 BID and placebo of 4.2 on the NRS scale.

WOMAC pain-subscore difference	Common SD	Power
3.8	9	0.87
	11	0.72
	13	0.57
4.0	9	0.90
	11	0.76
	13	0.61
4.2	9	0.93
	11	0.80
	13	0.66

Table 2 Power calculations for pairwise difference in WOMAC pain sub-score between AMZ001 andplacebo with 108 evaluable subjects per group, 5 % level of significance, two-sided.

The power is not adjusted for multiple comparisons and adjustment for multiplicity will not be made as there is one test only performed for the primary endpoint.

It should be noted that the current trial is not designed or powered to evaluate superiority of AMZ001 compared to Voltaren® gel, but the trial will provide important information on onset and duration of action of AMZ001 to guide future, larger trials. Also, the trial is not powered to evaluate superiority of AMZ001 applied twice daily as compared to once daily, but the trial will provide information on efficacy, safety, and tolerability of twice daily administration as compared to once daily administration.

Furthermore, the trial will be used to finalize the psychometric validation of the Pain Diary and the Satisfaction Questionnaire.

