#### 4.2.2.1 Secondary endpoints

#### **WOMAC Osteoarthritis Index**

The WOMAC Osteoarthritis Index consists of 24 questions about aspects of the target knee over the previous 24 hours. The questions are split into three sections: *Pain, Stiffness* and *Difficulty Performing Daily Activities* (i.e. Physical Function). Each question is scored on a 0-10 11-point numerical scale, where higher numbers indicate greater pain, stiffness or difficulty in performing daily activities.

WOMAC scores	Range (min – max)	Derivation
Total score	0 - 240	Q1 + Q2 + + Q23 + Q24
Pain sub-score	0 - 50	Q1 + Q2 + Q3 + Q4 + Q5
Pain weight bearing sub-score	0 - 30	Q1 + Q2 + Q5
Pain non-weight bearing sub-score	0 - 20	Q3 + Q4
Stiffness sub-score	0 - 20	Q6 + Q7
Function sub-score	0 - 170	Q8 + Q9 + + Q23 + Q24

The following scores are derived from answers to the WOMAC questionnaire:

For convenience and ease of interpretation, all WOMAC derived scores will be normalised to a 0-100-point scale for data analysis where, for each score

#### normalised score = (score/max possible value) \* 100

The full WOMAC questionnaire is assessed for the target knee at baseline (Visit 2), week 1 (Visit 3) and weeks 2, 3 and 4.

The WOMAC pain sub-scale is also completed at screening for both the left/right hips and the left/right knees. This is for the assessment of baseline status and eligibility, the determination of the target knee and whether the subject has bilateral or unilateral knee OA.

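### The SAP's worked example of an OMERACT-OARSI non-responder contradicts the rule it illustrates: with function missing, the rule usually gives a missing response.

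*SAP*

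**What the plan says.** SAP 4.2.3.1 gives two routes to response. Route (a) is high improvement in at least one "of the WOMAC pain or function sub-scores". Route (b) is moderate improvement in at least two of pain, function and PGA. High means at least 50% relative and at least 20 points absolute improvement; moderate means at least 20% and at least 10 points. Absolute changes are on normalised scores, and SAP 4.2.2.1 states that "all WOMAC derived scores will be normalised to a 0-100-point scale for data analysis".

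Three bullets cover subjects with one or more of the three scores missing:

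- The first classifies a subject as a responder if the available scores already meet the criteria.
- The second assigns non-response when the available scores do not meet them and "there is no possibility that they could have been a responder when considering possible values for the missing score(s". Its example reads, in part: "not achieve moderate response on either the WOMAC pain sub-score or the PGA and the WOMAC function sub-score missing then the subject is a non-responder".
- The third sets the response to missing when the missing score could have made the subject a responder. Its example reads "If either of the WOMAN pain or function sub-scores are missing then the response rate will be set to missing".

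The derivation is used repeatedly: "OMERACT-OARSI responder criteria will be evaluated at weeks 1, 2, 3 and 4". SAP 1.1.2 lists "OMERACT-OARSI responder rate at week 4" among the secondary endpoints.

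**The concern.** In the second bullet's example the missing score is function, one of the two scores that can establish response by itself under route (a). Response therefore cannot in general be ruled out, and the third bullet should apply instead of the second. One data pattern gets two outcomes, depending on whether the programmer follows the rule or its example.

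The coding would differ at any of the four visits where the pattern occurs. SAP section 5 requires independent parallel programming of efficacy endpoints, but that reveals the problem only if the two programmers follow different sentences. If both follow the example, the outputs agree and the misclassification passes unnoticed.

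**Working it through.** **Inputs.** The routes, thresholds and bullets are those of SAP 4.2.3.1. The function sub-score runs from 0 to 170 raw (SAP 4.2.2.1). SAP 2.2, Table 2, is calculated "with 108 evaluable subjects per group".

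**Control.** Applying the three bullets mechanically to the first bullet's example (high improvement in pain, function and PGA missing) gives responder, as the SAP says. The second bullet's example does not reproduce.

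**The example at category level.** Pain and PGA are both below moderate and function is missing.

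| Possible function improvement | Route (a) | Route (b) | Outcome |
|---|---|---|---|
| below moderate | no | 0 of 2 | non-responder |
| moderate | no | 1 of 2 | non-responder |
| high | yes | 1 of 2 | responder |

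The outcome depends on the missing score, so the rule gives missing. The example says non-responder.

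**The example at score level.** High improvement needs a normalised fall of 20, which is 20 × 170/100 = 34 raw points, and a fall of at least half the baseline. From baseline b the final score must satisfy 0 ≤ final ≤ min(b − 34, b/2), which is possible only if b ≥ 34.

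- Baseline 34 to 170: 170 − 34 + 1 = 137 of 171 possible scores. The rule gives missing, so the example conflicts with it.
- Baseline 0 to 33: 34 of 171 possible scores. High improvement is unattainable and the example agrees with its rule.

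These are counts of possible scores, not of subjects. The example states no baseline condition.

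**The other reading of the example.** Suppose it means failing only one of pain and PGA, with the other at moderate. Moderate improvement in function would then complete route (b). That needs a fall of 10 × 170/100 = 17 raw points, possible from baseline 17, so the conflict covers 170 − 17 + 1 = 154 of 171 scores.

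**Effect on the rate.** Let k of N = 108 subjects in an arm show the pattern, and let p be the response rate among the other N − k. If the rate is taken among non-missing subjects, following the rule gives p and following the example gives p(N − k)/N. The gap is pk/N. With p assumed to be 45-60%:

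- k = 1: 0.45/108 = 0.42 to 0.60/108 = 0.56 percentage points
- k = 2: 0.83 to 1.11 points
- k = 3: 1.25 to 1.67 points

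For an assumed 60% versus 45%, the rule gives a difference of 15.0 points. The example gives 60(108 − k₁)/108 − 45(108 − k₀)/108:

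| Affected (active, placebo) | Difference, points |
|---|---|
| 1, 1 | 14.86 |
| 3, 3 | 14.58 |
| 1, 0 | 14.44 |
| 0, 1 | 15.42 |
| 3, 0 | 13.33 |
| 0, 3 | 16.25 |

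With k = 0 there is no effect. If the denominator is all mITT subjects, the rate is the same under both codings and only the number reported as missing changes.

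**The replacement example.** PGA is missing and pain and function are both below moderate. Route (a) fails because any high improvement is also a moderate one. Route (b) fails because PGA can supply only one of the two scores needed. The outcome is non-response at all 11 possible PGA baselines. At category level this is the only single-missing pattern for which the rule gives non-response.

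**The case against.** The strongest reply is that the faulty text is only an illustration in parentheses, while the rule beside it is complete and clear and double programming is required. The pattern is also narrow. Pain and function come from one questionnaire completed at the same visits, so a subject who drops out or misses a visit would normally lack both. Nothing in the documents indicates that even one subject would have pain and PGA present with function missing. The counts of one to three, the response rates and the denominator are all assumed, and 108 is the evaluable number for the primary endpoint. Neither SAP 4.2.2.2 nor 4.2.3.2 names a model or denominator for the responder rate.

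All of this bears on size, and on size it stands. It does not remove the contradiction: the SAP nowhere says that the rule overrides its examples, and an example is what a programmer is likely to test code against.

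A further fair point is that the third bullet's example is too broad if read on its own. It would set the response to missing whenever pain or function is missing, including the first bullet's example, where function is missing and the subject is correctly a responder. It is right only within its own bullet's condition. The contradiction therefore rests on route (a) and the second bullet's rule, and does not need the third bullet's example as support.

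**Conclusion.** The concern holds. As written, the example misapplies its own rule unless baseline function is below 20 on the 0-100 scale. Few subjects are likely to start that low, since inclusion criterion 5 requires target-knee pain of at least 20 of 50 at screening (40 normalised). That is an inference, because no entry criterion is set for function.

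The practical impact is probably minor. It is at most 1.67 percentage points on one arm's rate with up to three affected subjects, given 108 per arm, a rate of 45-60% and a denominator of non-missing subjects. Equal numbers affected in both arms, up to three, move an assumed 15-point difference by no more than 0.42 points (15.00 − 14.58). The larger shifts need the affected subjects to fall in one arm only. The number affected cannot be derived from the documents.

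**What to change.** In SAP 4.2.3.1, replace the second bullet's example with this one: neither pain nor function reaches moderate improvement and PGA is missing, so the subject is a non-responder. Add a sentence stating that the three-bullet rule governs and that the examples only illustrate it; this also contains the over-broad example in the third bullet. Make the change before unblinding, so that the coding cannot be chosen with results in view.

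The cost is a small wording change in the SAP. It needs no new data or analysis and leaves the sample size and primary endpoint as they are. Subjects with the affected pattern and baseline function of 34 of 170 or more become missing instead of non-responders, so slightly fewer subjects are classified.

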### 4.2.3.2 Summary presentations and methods of analysis

Summaries and analysis will be performed for the mITT set only.

For the following QoL endpoints, absolute values and absolute change from baseline will be summarized over time by treatment group. Statistical analysis will be conducted as for the primary efficacy analysis using a mixed effects repeated measures model.

- WPAI % time missed
- WPAI % impairment while working
- WPAI % overall work impairment
- WPAI % activity impairment
- EQ5D VAS

### 4.3 Safety

Safety parameters will be evaluated for the safety analysis data set.

#### 4.3.1 Adverse events

Adverse events (AEs) will be classified according to MedDRA version 21.0.

An AE overview summary table will be prepared including the number of subjects reporting an AE, the percentage of subjects (%) with an AE, and the number of events (E) reported for the following categories:

- Treatment-emergent AEs
- Deaths
- Serious adverse events (SAEs)
- AEs leading to withdrawal of study drug
- Severe and life-threatening AEs
- Adverse drug reactions

Treatment emergent AEs are defined as any AE that has occurred after the first administration of IMP administration.

ADRs are defined as all untoward and unintended responses to an IMP related to any dose administered, i.e. all AEs which are probably or possibly related to IMP.

Treatment-emergent AEs will be summarized in a table by dictionary level, i.e., system organ class (SOC) and preferred term (PT) for MedDRA. The table will display the total number of subjects reporting an AE, the percentage of subjects (%) with an AE and the number of events (E)

reported. AEs will be presented by SOC sorted alphabetically and PT sorted in decreasing frequency of occurrence.

Pre-treatment AEs will be listed only.

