**Planned trial and treatment duration per subject:**

The treatment phase consists of four weeks of treatment with one baseline (Day 1) visit and 4 weekly visits, followed by a follow-up visit two weeks after last application of IMP. The screening period is up to 21 days from the time of providing written consent. In total, the expected duration of the trial participation of a randomized subject will be up to 63 days.

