6. Assessed without analgesic medication for five half-lives of the analgesic.
7. WOMAC assessment of hips should only be performed at the screening visit.
8. To be completed daily in the evening during the first week of treatment, i.e. between Visit 2 and Visit 3. In the period between other subsequent visits, the questionnaire will be completed during the evening of the day prior to the next visit.
9. Only weight collected.
10. Conditions previously unknown to the subject at the time of the screening visit will be recorded as medical history. All subsequent events will be recorded as adverse events.
11. To be collected/dispensed if previously dispensed supply of rescue medication was depleted and empty packaging returned to site.
12. Collection of remaining rescue medication at Visit 6. Empty packaging of previously dispensed kit should be returned to the site if new rescue medication is requested.
13. Serum test at screening visit, urine dipstick at all other visits.
14. To be done after IMP application and questionnaire/test completion (approximately 1-2 hours after IMP application). Exact time of IMP application and time of blood sampling must be documented.
15. Dispensation is not mandatory for subjects allocated to Voltaren® gel

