- 1. If subject is washed out of analgesics at Screening Visit 1a, the examinations scheduled for screening visits 1a and 1b can be performed on the same day.
- 2. Phone call.
- 3. Skin assessment to be performed prior to application of study drug at baseline visit.
- 4. Subjects will be educated on appropriate expectations around their participation in a clinical study and the importance of reliably consistently and accurately reporting their pain throughout the study.
- 5. WOMAC pain sub-score (5 questions) to be assessed on a daily basis on paper at home during first week of treatment, i.e. the period between Visit 2 and Visit 3.
- 6. Assessed without analgesic medication for five half-lives of the analgesic.
- 7. WOMAC assessment of hips should only be performed at the screening visit.

- 8. To be completed daily in the evening during the first week of treatment, i.e. between Visit 2 and Visit 3). In the period between other subsequent visits, the questionnaire will be completed during the evening of the day prior to the next visit.
- 9. Only weight collected.
- 10. Conditions previously unknown to the subject at the time of the screening visit will be recorded as medical history. All subsequent events will be recorded as adverse events.
- 11. To be collected/dispensed if previously dispensed supply of rescue medication was depleted and empty packaging returned to site.
- 12. Collection of remaining rescue medication at Visit 6. Empty packaging of previously dispensed kit should be returned to the site if new rescue medication is requested.
- 13. Serum test at screening visit, urine dipstick at all other visits.
- 14. To be done after IMP application and questionnaire/test completion (approximately 1-2 hours after IMP application). Exact time of IMP application and time of blood sampling must be documented.
- 15. Dispensation is not mandatory for subjects allocated to Voltaren® gel

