#### Summary tables will be prepared for:

- All TEAEs
- All non-serious TEAEs
- TEAEs by causality (related/unrelated)
- TEAEs by severity
- TEAEs leading to death
- TEAEs leading to withdrawal of study drug
- Treatment emergent SAEs

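### The treatment-emergent definition in SAP 4.3.1 has no worsening clause, so an AE that starts in screening and worsens on gel drops out of the TEAE tables unless the worsening is entered as a new record

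*SAP*

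**What the plan says.** SAP 4.3.1 classifies AEs by when they occur: "Treatment emergent AEs are defined as any AE that has occurred after the first administration of IMP administration". The same section adds: "Pre-treatment AEs will be listed only". Nothing there covers an event already present at the first application that later becomes more severe or serious.

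AE recording begins before treatment. The schedule of procedures (Protocol Table 2, SAP Table 1) marks adverse events at Screening 1a and 1b. Footnote 10 separates two cases. For what comes to light at the screening visit it says: "Conditions previously unknown to the subject at the time of the screening visit will be recorded as medical history". For what follows it says: "All subsequent events will be recorded as adverse events". On the length of this period the protocol synopsis says: "The screening period is up to 21 days from the time of providing written consent".

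The table by system organ class and preferred term, and each of the seven summary tables listed in SAP 4.3.1 (for example "TEAEs by severity"), are limited to treatment-emergent events. The AE overview table is worded differently. Only its first row is treatment-emergent. The rows for deaths, serious events, withdrawals of study drug, severe or life-threatening events and adverse drug reactions carry no such limit, and adverse drug reactions are defined as "all AEs which are probably or possibly related to IMP".

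**The concern.** Subjects enter on regular oral NSAID or paracetamol and wash out analgesics around screening (Protocol inclusion criteria 5 and 8), so an AE that is open at the first application is foreseeable. If such an event becomes worse on gel, the timing rule still calls it pre-treatment.

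The kind, frequency and severity of AEs is a stated safety endpoint (SAP 1.1.2), and aggravation of an existing complaint is one way in which an effect of the drug could show. A definition based on first occurrence alone leaves that aggravation out of the severity, causality, withdrawal and serious-event tables. It also leaves two sets of tables that may not reconcile, because most overview rows do not use the same restriction.

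**Working it through.** **1. Can an AE be open before the first application?** The inputs are screening of up to 21 days and follow-up two weeks after the last application (Protocol synopsis, planned duration), and treatment of 28 days (SAP 2). Then 21 + 28 + 14 = 63 days, which reproduces the protocol's stated maximum participation. Screening is therefore up to 21/63, or one third, of participation. With footnote 10, pre-treatment AE records can exist. They are limited to events after the screening visit, since conditions that come to light at that visit become medical history. Twenty-one days is a maximum; visits 1a and 1b may fall on the same day.

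**2. Follow one event.** Take mild dyspepsia that begins between screening and baseline and turns severe in week 2, held as one AE record with its screening onset.

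| Output | Restriction as worded | Is the worsened event shown? |
|---|---|---|
| Table by organ class and preferred term | Treatment-emergent | No |
| Seven summary tables | Treatment-emergent | No |
| Overview, first row | Treatment-emergent | No |
| Overview, rows for deaths, serious, withdrawal, severe, adverse drug reaction | None stated | Possibly, if it meets the row's criterion; the listing-only rule pulls the other way |
| AE listings | Only the pre-treatment listing is limited by timing | Yes |
| Skin, laboratory, vital-sign and ECG summaries (SAP 4.3.2) | Independent of AE timing | Only a change that is measured there; dyspepsia is not |

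**3. Change the recording convention.** If the worsening is entered as a new AE dated after the first application, it satisfies the existing definition and enters every relevant table. The number lost is then zero. The text reviewed does not say which convention applies.

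**4. Consistency.** Under the single-record convention, an event that becomes serious on gel can be counted in the overview row for serious events and be absent from the table of treatment-emergent serious events.

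**5. Size.** The documents give no rates, so these are assumptions only.

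- Suppose 10% to 15% of subjects have an AE in screening and 10% to 20% of those worsen on treatment. The joint rate runs from 0.10 × 0.10 = 1% to 0.15 × 0.20 = 3%.
- Per double-blind arm of 120: 120 × 0.01 = 1.2 to 120 × 0.03 = 3.6 subjects.
- On AMZ001, two arms, 240 subjects: 2.4 to 7.2.
- A wider joint rate of 0.5% to 5% gives 0.6 to 6 per arm of 120, and 2.2 to 22 of all 440.
- If worsening opens a new record: 0.

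These are counts of events left out. They do not measure bias between arms, which would be only the excess on active gel over placebo, and nothing in the documents allows that to be estimated.

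**The case against.** The strongest reply is that the loss depends on a recording rule that is not visible. The protocol text available is the synopsis, which refers to Section 8.3.3 for safety endpoints, and neither the AE recording rules nor the CRF instructions can be checked. The SAP says occurred, not started, so under a new-record convention the present wording already works. This stands, and the conclusion is conditional on it.

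Second, a reader might infer that a worsened event disappears into a listing even when it is serious, severe or leads to withdrawal. The documents do not support that. Five overview rows are not worded as treatment-emergent only, and the listings of serious events, deaths and withdrawals are not limited by timing. What is left is an ambiguity between those rows and the listing-only sentence.

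Third, some obvious examples are largely covered elsewhere. Redness at the planned application site is an exclusion (criterion 16), eligibility is rechecked at baseline, and skin is assessed at baseline and at each on-treatment visit and summarized by visit and arm. Blood pressure is measured at screening, baseline and all four on-treatment visits and summarized in the same way as laboratory values, including change from baseline. This also stands, although those summaries carry no information on seriousness, causality or withdrawal, and a complaint such as dyspepsia has no summary of its own.

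Finally, it is tempting to say that the definition makes AMZ001 look safer. That would follow only if active gel worsens screening-onset events more often than placebo, which the documents do not show.

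**Conclusion.** The gap in the definition is real. As SAP 4.3.1 is worded, and if a worsening is kept on the original record, an AE that starts in screening and worsens on gel has no route into the table by organ class and preferred term or into the seven TEAE tables, and those tables can disagree with the overview.

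The reach is limited. Such an event may still appear in five overview rows and does appear in the listings; skin, laboratory, vital-sign and ECG changes are reported separately. The number affected is unknown and probably small: zero to a few subjects per arm, on assumed rates. The effect is confined to safety reporting and does not touch the primary endpoint or the power. No direction of bias between arms can be claimed. The point deserves correction because the rule is explicit, it bears on a stated safety endpoint, and the repair is cheap.

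**What to change.** In SAP 4.3.1, define a treatment-emergent AE as one with onset on or after the first IMP application, or one with earlier onset that increases in severity or becomes serious after the first application. Treat as pre-treatment, and list only, those AEs that did not worsen. Apply the same rule to every row of the overview table so that it reconciles with the TEAE tables.

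Withdrawal of study drug should not by itself make an unchanged pre-treatment AE treatment-emergent. Such an event remains visible in the withdrawal listing.

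Before unblinding, confirm and state in the SAP how worsening is recorded. If each worsening opens a new record with its own date, one sentence saying so is enough. If the CRF holds a single severity per AE, query the AEs that were ongoing at Visit 2 for severity and seriousness before and after the first application.

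The cost is one derivation, a change of wording and a few data queries.
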